16.1.2 Analysis

All summaries and listings for safety parameters (adverse events (AEs) will be based on the SAF population.

In order to be able to compare the neonatal vaccine schedule to the infant vaccine schedule after 3 doses of RV3-BB, due to the different time points of vaccination between the two different schedules, summaries of AEs are presented based on doses 1-3 of investigational product for the neonatal schedule and doses 2-4 of investigational product for the infant schedule. Hence, only AEs that started after the time of administration of the investigational product up to 28 days following each dose will be summarised for doses 1, 2 and 3 for the neonatal comparison and for doses 2, 3 and 4 for the infant comparison. In addition, some summaries will be presented by dose with an overall summary of AE (as presented for the DSMB).

Summaries (and listings where applicable) will be presented for all participants. For summaries, all safety data will be presented by dose number unless otherwise specified.

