6.5 Visit 3 (Week 6 +7 days)

The following will be performed/recorded at the trial site no earlier than 6 weeks of age:

- Review AEs.
- Review concomitant medication.
- Review feeding status.
- Review Diarrhoea Log and study reminder card.
- Collect a pre dose blood sample.
- Collect a saliva sample.
- Vital signs (see section 8.3) within the 60 minutes pre dose.
- Administer 2mL of Mylanta Original® antacid formulation within the 10 minutes pre dose.
- Administer the IP dose.

The following procedures will be performed post dose;

- Administer IPV and any scheduled EPI vaccines other than OPV and rotavirus vaccines according to local guidelines (see section 9.2).
- Vital signs (see section 8.3) will be measured at 15 minutes and 30 minutes post dose (±5 minutes).
- Record any AEs.
- Issue kits and containers for stool and diarrhoea samples, and instructions for collection and storage of samples (see section 8.4).

Study staff will contact the parents/guardians (clinic or home visit) the day following dosing, and once on day 3, 4 or 5 following dosing, to review AEs and medications, and collect stool and diarrhoea samples.

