6.7 Visit 5 (Week 10 ±7 days)

The following will be performed/recorded at the trial site, no sooner than 21 days after the previous dose of IP (Visit 3):

- Review AEs.
- Review concomitant medication.
- Review feeding status.
- Review Diarrhoea Log and study reminder card.
- Collect a pre dose blood sample.
- Collect a saliva sample.
- Vital signs (see section 8.3) within the 60 minutes pre dose.
- Administer 2mL of Mylanta Original® antacid formulation within the 10 minutes pre dose.
- Administer the IP dose.

The following procedures will be performed post dose;

- Administer IPV and any scheduled EPI vaccines other than OPV and rotavirus vaccines according to local guidelines (see section 9.2).
- Vital signs (see section 8.3) will be measured at 15 minutes and 30 minutes post dose (±5 minutes).
- Record any AEs.
- Issue kits and containers for stool and diarrhoea samples, and instructions for collection and storage of samples (see section 8.4).

Study staff will contact the parents/guardians (clinic or home visit) the day following dosing, and once on day 3, 4 or 5 following dosing, to review AEs and medications, and collect stool and diarrhoea samples.

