6.9 Visit 7 (Week 14 ±7 days)

The following will be performed/recorded at the trial site, no sooner than 21 days after the previous dose of IP (Visit 5):

- Review AEs.
- Review concomitant medication.
- Review feeding status.

- Review Diarrhoea Log and study reminder card.
- Collect a pre dose blood sample
- Collect a saliva sample
- Vital signs (see section 8.3) within the 60 minutes pre dose.
- Administer 2mL of Mylanta Original® antacid formulation within the 10 minutes pre dose.
- Administer the IP dose.

The following procedures will be performed post dose;

- Administer IPV and any scheduled EPI vaccines other than OPV and rotavirus vaccines according to local guidelines (see section 9.2).
- Vital signs (see section 8.3) will be measured at 15 minutes and 30 minutes post dose (±5 minutes).
- Record any AE.
- Issue kits and containers for stool and diarrhoea samples, and instructions for collection and storage of samples (see section 8.4).

Study staff will contact the parents/guardians (clinic or home visit) the day following dosing, and once on day 3, 4 or 5 following dosing, to review AEs and medications, and collect stool and diarrhoea samples.

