6.11 Visit 9 (Week 18 ±7 days)

The following will be performed/recorded at the trial site, no sooner than 21 days after the previous dose of IP (Visit 7):

- Review AEs.
- Review concomitant medication.
- Review feeding status.
- Review Diarrhoea Log.
- Collect a pre dose blood sample.
- Vital signs (see section 8.3) within the 60 minutes pre dose.
- Administer Rotarix®.
- Administer any scheduled EPI vaccines according to local guidelines (see section 9.2).

Study staff will contact the parents/guardians (clinic or home visit) the day following dosing.

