10.5 Doses and treatment regimens

Approximately 688 participants will be prospectively randomised to one of the following four treatment groups in a 1:1:1:1 ratio.

- High dose neonatal RV3-BB vaccine schedule (1x10⁷titre dose). RV3-BB Vaccine for doses 1, 2 and 3 and placebo for dose 4
- Mid dose neonatal RV3-BB vaccine schedule (3x10⁶titre dose). RV3-BB Vaccine for doses 1, 2 and 3 and placebo for dose 4.
- Low dose neonatal RV3-BB vaccine schedule (1x10⁶titre dose). RV3-BB Vaccine for doses 1, 2 and 3 and placebo for dose 4.
- High dose Infant RV3-BB vaccine schedule (1x10⁷titre dose). Placebo for dose 1 and RV3-BB Vaccine for doses 2, 3 and 4

Participants will also receive a dose of commercially available Rotarix® at 18 weeks of age.

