3.1.2 Safety and tolerability endpoints

Safety and tolerability will be assessed through:

- Unsolicited Adverse Events (AE) in the days 0-28 following each dose of IP.
- Serious Adverse Events (SAE) from the first dose of IP until 28 days post last dose of IP.
- Review of episodes of blood in stool.

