7.1.1 Visit and date conventions

Visit day will be calculated from the reference treatment start date which will be used to present start/stop day of assessments and events. The reference treatment start date is defined as the date of first IP administration. The following conventions will be used for visit references:

- Visit day = date of event reference treatment start date
- Visit week = $\frac{visit \, day}{7}$, rounding up to next whole number

No visit windowing (i.e. remapping of visits based on visit windows) will be performed for this trial. The assigned nominal visit will be used for by-visit summaries. In the situation where the assessment/event date is partial or missing, visit day/week/month, and any corresponding durations will appear missing in the data listings. Unscheduled measurements will not be included in by-visit summaries. Trial visit will be assigned as below (see section 4.3, Schedule of Events):

Pre-study: Second trimester to birth

Preliminary consent, cord blood collection and maternal blood sampling will happen during this period.

Visit 1 (Day 1; birth to 144 hours old)

Participants will return to the trial site for Day 1 procedures and maternal blood samples will be collected.

Visit 2 (Day 8; 7±1 days post visit 1), Visit 4 (Week 7; 7±1 days post visit 3), Visit 6 (Week 11; 7±1 days post visit 5), Visit 8 (Week 15; 7±1 days post visit 7)

Participants will return to the trial site for vital sign measurements, feeding review, AE and concomitant medication recording.

Visit 3 (Week 6; + 7 days), Visit 5 (Week 10; \pm 7 days and at least 21 days post visit 3), Visit 7 (Week 14; \pm 7 days and at least 21 days post visit 5), Visit 9 (Week 18; \pm 7 days and at least 21 days post visit 7)

Participants will return to the trial site for Week 6/10/14/18 procedures.

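### The 28-day AE windows in SAP 16.1.2 can overlap by up to 7 days after doses 2 and 3, and the SAP does not say which dose an AE in the overlap belongs to

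*SAP*

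**What the plan says.** **The AE window.** SAP 16.1.2 limits the AE summaries: "only AEs that started after the time of administration of the investigational product up to 28 days following each dose will be summarised". It applies this to doses 1, 2 and 3 in the neonatal schedule and doses 2, 3 and 4 in the infant schedule, so that both schedules are described over their three RV3-BB doses. Unless otherwise specified, safety summaries are by dose number. SAP 3.1.2 words the endpoint as "Unsolicited Adverse Events (AE) in the days 0-28 following each dose of IP".

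**The spacing of doses.** Protocol 6.7 places Visit 5 (dose 3) "no sooner than 21 days after the previous dose of IP (Visit 3"). Protocol 6.9 places Visit 7 (dose 4) "no sooner than 21 days after the previous dose of IP (Visit 5"). Protocol 6.11 places Visit 9, the Rotarix visit, "no sooner than 21 days after the previous dose of IP (Visit 7"). The nominal times are weeks 6, 10, 14 and 18.

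**The products.** Under Protocol 10.5 each neonatal arm receives "RV3-BB Vaccine for doses 1, 2 and 3 and placebo for dose 4". The infant arm receives placebo at dose 1 and RV3-BB at doses 2 to 4.

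**What is not said.** Neither document cuts a window at the next product or says which dose receives an AE that falls in two windows. Protocol 13.4.2 counts a preferred term once per participant when incidence is calculated, but it does not allocate the event to a dose.

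**The concern.** A window that runs to day 28 does not fit between doses that may be 21 days apart. Suppose dose 2 is given at age 46 days, dose 3 at age 70 days, and vomiting starts at age 72 days. The event starts on day 26 after dose 2 and day 2 after dose 3, and satisfies the rule for both.

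By-dose tables are the main form of the safety output: SAP 16.1.3 to 16.1.9 ask for incidence or event numbers by dose for all AEs, severity, relatedness, SAEs, withdrawals and deaths. Two programmers following SAP 16.1.2 could produce different tables, and an acute reaction to one dose could also appear under the dose before it.

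The last neonatal RV3-BB window raises a second problem. Dose 4 in those arms is placebo, given at a visit where IPV and any scheduled EPI vaccines are also given (Protocol 6.9). An AE starting after that visit but within 28 days of dose 3 enters the RV3-BB dose-3 summary. SAP 16.1.2 restricts the neonatal summaries to doses 1 to 3 in order to describe the RV3-BB doses, and the overlap works against that purpose.

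**Working it through.** The plan states no figure for overlap, so there is none to reproduce. The check uses the visit windows only.

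**Inputs, as age in days**
- Dose 1: 0 to 6 (SAP 7.1.1, "Visit 1 (Day 1; birth to 144 hours old").
- Dose 2: 42 to 49 (Protocol 6.5, week 6 + 7 days, "The following will be performed/recorded at the trial site no earlier than 6 weeks of age").
- Dose 3: 70 ± 7 = 63 to 77. Dose 4: 98 ± 7 = 91 to 105. Rotarix: 126 ± 7 = 119 to 133. Each is at least 21 days after the previous dose (Protocol 6.7, 6.9, 6.11).

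**Permitted gaps g**
- Dose 1-2: 42 − 6 = 36 to 49 − 0 = 49 days.
- Dose 2-3: the windows alone allow 63 − 49 = 14, raised to 21 by the minimum; the longest is 77 − 42 = 35.
- Dose 3-4: the windows alone allow 91 − 77 = 14, raised to 21; the longest is 105 − 63 = 42. Dose 4 to Rotarix has the same range.

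**Overlap for a gap g**
- Elapsed time: max(0, 28 − g). At g = 21 this is 7 of 28 days (25%).
- Inclusive days 0 to 28: max(0, 29 − g). At g = 21 this is 8 of 29 days (28%). At g = 28 one calendar day is still shared.
- Dose 1-2: max(0, 29 − 36) = 0, so no overlap on either reading.
- Both later gaps can be 21 days in one infant (ages 49, 70, 91), which gives 7 + 7 = 14 doubly covered days across RV3-BB doses 2 to 4 in the infant arm.

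**How often a permitted gap overlaps.** The documents give no attendance data. Enumerating every permitted set of ages at Visits 3, 5, 7 and 9 gives 14,764 sequences. With equal weights:

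| Pair | Gap under 28 days | Gap 28 days or less |
|---|---|---|
| Dose 2-3 | 10,192 / 14,764 = 69% | 11,348 / 14,764 = 77% |
| Dose 3-4 | 7,952 / 14,764 = 54% | 9,108 / 14,764 = 62% |

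Weighting each pair of dates equally, one pair at a time, gives 56/92 = 61% and 64/92 = 70% for dose 2-3, and 77/197 = 39% and 92/197 = 47% for dose 3-4. The shares depend on the weighting; the 7-day maximum does not.

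**Which other product can fall in a summarised window**
- Neonatal arms: placebo dose 4 can fall in the dose-3 window. Rotarix cannot, since Visit 9 is at least 21 + 21 = 42 days after dose 3.
- Infant arm: placebo cannot, since it precedes the first RV3-BB dose by at least 36 days. Rotarix can fall in the dose-4 window.

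**The case against.** **Double counting is inferred.** SAP 16.1.2 is worded as an inclusion filter and does not say that an AE is shown under every dose it qualifies for. Protocol 13.4.2 protects per-participant incidence, the overall summary in SAP 16.1.3 is separate from the by-dose tables, and the separate output templates, not available here, might contain a rule. This stands as far as it goes: the documents show that an AE could be counted under two doses, not that it will be. It does not supply the missing allocation.

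**Rotarix reactions.** A reader might infer that the infant arm's AE tables absorb Rotarix reactions over the whole overlap. The documents do not support that. Protocol 11.3 ends routine AE capture at the final study visit, and Protocol 6.11 lists the AE review before Rotarix with no recording step after it, unlike the IP dosing visits. What can enter is an event on the Visit 9 day, possibly one reported at the next-day contact (whose purpose is not stated), and SAEs to 28 days after the last IP dose (SAP 3.1.2). An overlap in days for dose 4 to Rotarix would count days on which AEs are not routinely collected, so none is given here.

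**Causality.** A reader might also infer that placebo or Rotarix reactions become RV3-BB reactions. Falling in a time window is not a relatedness judgement; the investigator makes that separately (Protocol 11.1, SAP 16.1.5).

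**Limited consequence.** SAP 7.1.4 plans no formal testing of safety data. The three neonatal titre arms share one schedule, so the overlap builds in no imbalance between titres. Both points stand and limit the weight of the concern.

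**The narrower reading.** On elapsed time, a dose given exactly 28 days later creates no overlap. That is why the under-28 figures are given first. However, Protocol 11.3 asks for AE start dates and does not mention times, so onset on a dosing day may not be orderable.

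**Conclusion.** The concern holds for the by-dose AE tables and for any event total formed by adding over doses. The windows after doses 2 and 3 can overlap the next dose's window by up to 7 elapsed days, or 8 of 29 inclusive days; this follows from the documents alone. The 69% and 54% (77% and 62% at 28 days or less) rest on equal weighting of all permitted visit sequences. They describe intervals and must not be read as the proportion of AEs double counted, which cannot be estimated without attendance and AE onset data.

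The wrong-product problem is clearest in the neonatal arms, where AEs after the placebo dose-4 visit can be tabulated under RV3-BB dose 3. In the infant arm the Rotarix route is narrow. The overlap does not inflate per-participant overall incidence, and it does not touch investigator causality or the primary endpoint. The change should be made before the tables are programmed, because the stated window conflicts with the SAP's own aim of summarising the three RV3-BB doses.

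**What to change.** In SAP 16.1.2:
- assign each AE to the most recent product given before onset;
- end each dose's window at the earlier of day 28 and the next IP or Rotarix administration;
- state a convention for onset on a dosing day, and align the wording with days 0-28 in SAP 3.1.2;
- count each event once in totals;
- list any AE starting after Rotarix separately.

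Two passages bear on the derivation and should be reconciled. SAP 13.1.1 gives the Visit 5 and Visit 7 windows without the 21-day minimum, which alone would permit a 14-day gap. Rotarix timing after withdrawal differs between footnote 7 of Protocol Table 1 and Protocol 6.12.1.

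The cost is SAP wording and one derivation rule; no new data or visits are needed. The downside is unequal windows: those after doses 2 to 4 become 21 to 28 days for infants given the next product early, while dose 1 keeps 28. Neonatal doses 1 to 3 and infant doses 2 to 4 would then differ somewhat in follow-up, so the tables should report the actual window length by dose and arm. A lighter alternative is to keep the overlapping windows, say so in the tables, and count each event once in totals. That removes double counting from the totals but leaves post-placebo AEs under RV3-BB dose 3.

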16.1.3 Incidence of AEs and SAEs

AEs defined in section 16.1.1 and Serious AEs is defined as AEs for which seriousness is indicated as "Yes". In cases where seriousness criteria are missing, the worst-case scenario will be assumed. The incidence of all SAEs and AEs by MedDRA System Organ Class (SOC) and Preferred Term (PT) will be presented by dose number and treatment group. In addition, an overall summary will be presented indicating the following counts:

- Participants with at least one AE
- Participants with at least one SAE
- Participants with at least one grade 3/4 AE

- Participants with AEs leading to death
- Participants with AEs leading to early withdrawal from trial
- Participants with at least one IP related AE
- Participants with at least one IP related grade 3/4 AE
- Total number of AEs
- Total number of grades 3/4 AEs
- Total number of IP related AEs (assessed as possibly, probably or definitely related to IP)
- Total number of Investigational Product-related grade 3/4 AE (assessed as possibly, probably or definitely related to IP)

16.1.4 AEs by severity

The incidence (%) and number of events of all AEs will be presented by SOC, PT, severity and dose number for each treatment group.

16.1.5 Investigational Product-related AEs

AEs relatedness to IP (determined by the principal investigator) will be summarized per the following categories:

- Related ("Definitely related", "Probably related", "Possibly related")
- Not related ("Unlikely related", "Not related")

If relatedness is missing, the worst case will be assumed, i.e. related. The incidence (%) and number of events of all drug-related AEs will be presented by SOC, PT, relatedness and dose number for each treatment group.

16.1.6 Serious AEs

Serious AEs are defined in section 16.1.3. In cases where seriousness criteria are missing, the worst-case scenario will be assumed.

The incidence (%) and number of events of all serious AEs will be presented by SOC, PT and dose number for each treatment group. A data listing of serious adverse events (SAEs) will also be presented.

16.1.7 Investigational Product-related serious AEs

Serious Investigational Product-related AEs are defined as AEs for which seriousness is indicated as 'yes' and the relatedness defined as 'related' (see section 16.1.5). In cases where seriousness/relatedness criteria are missing, the worst-case scenario will be assumed, i.e. serious related AE.

The incidence (%) and number of events of all serious AEs will be presented by SOC, PT, relatedness and dose number for each treatment. A data listing of serious adverse events (SAEs) will also be presented.

16.1.8 AEs and related AEs leading to early withdrawal from study

The incidence (%) and number of events of all AEs and related AEs leading to early withdrawal will be presented by SOC, PT and dose number for each treatment. A data listing of AEs leading to early withdrawal from study will be presented.

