6.12 Discontinuation of Participants

6.12.1 Criteria for discontinuation

The participant may be discontinued from the trial at any time at the discretion of the investigator(s).

Specific reasons for withholding further doses or discontinuing a participant in this trial may include:

- Withdrawal of informed consent by parents/guardians.
- Participant lost to follow-up.
- Protocol non-compliance.
- Investigator considers that it is not in the interest of the participant to continue.
- MCRI terminates the study for administrative, financial or other reasons.

If a participant is discontinued from dosing, unless they withdraw consent they should continue to have blood samples collected at the scheduled time points and continue to collect diarrhoea samples and complete the Diarrhoea Log. Investigators are encouraged to discuss possible treatment discontinuations and withdrawals with the Medical Monitor, if appropriate, prior to ceasing treatment or withdrawing the infant. The decision to replace withdrawn subjects will be made on a case by case basis. Participants withdrawn due to AEs will not be replaced.

All withdrawn participants should be seen and assessed approximately 28 days after their last dose of IP, primarily for the purposes of monitoring participant safety. Wherever possible, AEs should be followed up until resolution. Parents/guardians who withdraw consent should be asked whether they agree to this follow up.

Participants who withdraw from study or IP will continue to receive IPV until the course is complete. They will receive Rotarix® at standard scheduled time points according to the National Immunisation Program.

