11.3 Recording of AEs

AEs will be captured from the time of first dose of IP until the final study visit. Parents/guardians will be asked at each visit whether their baby has experienced any AEs.

SAEs that are at least possibly or definitely related to IP occurring to a study participant after the AE reporting period will be reported to the sponsor if the Investigator becomes aware of them.

It is preferable that AEs are reported as diagnoses if one is able to be made, rather than individual signs and symptoms. The AE description, start and stop dates, severity, causality and outcome must be recorded, as well as any actions taken.

Unless a diagnosis is made, or signs and symptoms are present, an abnormal laboratory value or vital sign should only be reported as AEs if they cause the participant to discontinue from the trial, the investigator feels they are clinically significant, or they meet a criterion for a SAE.

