13.4.2 Adverse events

AE data will be listed individually and incidence of AEs summarised by system organ class and preferred terms within a system organ class for each treatment group. When calculating the incidence of AEs, each AE, based on preferred terminology defined by Medical Dictionary for Regulatory Activities (MedDRA; Version 13.1, or later), will be counted only once for a given participant. A summary of the number and percent of participants with the following treatment emergent AEs will be displayed by treatment groups:

- All AEs
- IP related AEs
- Severe AEs
- SAEs
- AEs leading to permanent discontinuation of IP.

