10.1.1 Variables and derivations

End of trial classifications are defined as follows:

• Early withdrawal: Participants who exited the trial prior to completion for any reason other than being lost to follow-up, such as adverse event, protocol deviation/violation, death, withdrawal by investigator, withdrawal of consent or any other reason.

Note: Participants who withdraw from study or IP will continue to receive IPV until the course is complete. They will receive Rotarix® at standard scheduled time points according to the National Immunisation Program.

- Completed trial: Participants that completed all trial visits, as indicated in the 'End of Study' (CRF page 55).
- Lost to follow-up: Participants who exited the trial prior to completion due to being lost to follow-up (CRF page 55).

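### The SAP replaces the protocol's summary of AEs that ended IP dosing with one of AEs that ended trial participation, and does not declare the change

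*SAP*

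**What the plan says.** Protocol 13.4.2 lists five treatment-emergent AE summaries, each giving the number and percent of participants by treatment group. The last is "AEs leading to permanent discontinuation of IP".

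SAP 16.1.3 has a different line in its overall summary: "Participants with AEs leading to early withdrawal from trial". SAP 16.1.8 adds a table, "The incidence (%) and number of events of all AEs and related AEs leading to early withdrawal will be presented by SOC", and a listing; the section title makes clear that the withdrawal is from the study. SAP 10.1.1 defines early withdrawal as "Participants who exited the trial prior to completion for any reason other than being lost to follow-up, such as adverse event" and further reasons. The other two end-of-trial classes there are lost to follow-up and completed, the latter being "Participants that completed all trial visits" as shown on the End of Study CRF page.

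Protocol 6.12.1 treats stopping doses and leaving the study as separate events: "If a participant is discontinued from dosing, unless they withdraw consent they should continue to have blood samples collected at the scheduled time points". It asks for diarrhoea samples and the Diarrhoea Log to continue as well. On data capture, Protocol 11.3 says: "The AE description, start and stop dates, severity, causality and outcome must be recorded, as well as any actions taken".

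**The concern.** In this trial, stopping IP and leaving the study are different states, and the protocol's summary concerns the first. A table of study withdrawals cannot stand in for it, because an infant who stops IP after an AE is meant to remain under observation. The more closely sites follow 6.12.1, the less the two groups overlap.

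Safety and tolerability is a stated secondary objective, and the trial compares three titres and two schedules. A reader of the study report will want to know, by arm, how often an AE ended dosing. Under the SAP, a zero in the withdrawal row means only that no infant left the study because of an AE. It could easily be taken to mean that no infant stopped IP because of one.

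The change is also undeclared. Protocol 13.3 commits to documenting departures from the planned analyses in the SAP. SAP section 5, where such changes belong, covers only the deferred exploratory work and the handling of cord-blood IgA. The revision history does not mention this change either.

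**Working it through.** No figure in the documents bears on this point, so the check is a comparison of texts.

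**Step 1: the five summaries in Protocol 13.4.2 against the SAP.**
- All AEs: present (16.1.3).
- IP-related AEs: present (16.1.3, 16.1.5).
- Severe AEs: present, as grade 3/4 counts (16.1.3) and AEs by severity (16.1.4).
- SAEs: present (16.1.3, 16.1.6).
- AEs that ended IP dosing: absent. The nearest items are the trial-withdrawal line in 16.1.3 and the table in 16.1.8.

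**Step 2: are the two categories the same?** No. SAP 10.1.1 ties early withdrawal to exit from the trial. Protocol 6.12.1 keeps infants who are off dosing in follow-up unless consent is withdrawn. The SAP itself recognises both states, since a note in 10.1.1 refers to participants withdrawing from either the study or IP, but it defines no end-of-trial class for the second.

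**Step 3: where does an infant who stops IP for an AE and stays in the study appear?**
- In the safety set, which needs only one dose of IP (SAP 6.1.2).
- In the general tables, which are also split by arm: "The incidence of all SAEs and AEs by MedDRA System Organ Class (SOC) and Preferred Term (PT) will be presented by dose number". The AE enters the severity and relatedness tables too and, if serious, the SAE tables. None of these depends on withdrawal. One separate limit applies: the schedule-comparison summaries in 16.1.2 take only AEs starting within 28 days of a dose.
- In the IP administration and compliance summaries (SAP 12.1.2, 13.1.2), which show missed doses but, as described, do not link them to an AE.
- Not in the 16.1.8 table or the matching line of 16.1.3.

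**Step 4: does any other planned summary link the AE to stopping IP?** None is described in SAP sections 10 to 16. The event is counted and the missed dose is visible, but the causal link that the protocol's fifth summary would report is not tabulated.

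**The case against.** The strongest reply is that little information is lost. The AEs are tabulated in full elsewhere. SAP 20.1.5 says that every eCRF variable with data should appear in the listings, so a recorded action on IP would be listed by participant. SAP 10.1.2 summarises exclusions from each analysis population with reasons, and an infant who misses an RV3-BB dose does not meet the per-protocol definition in 7.1.4. The last dose date is derived in 12.1.1. The documents' named safety endpoints are AEs, SAEs and blood in stool, and stopping IP is not among them. The table shells are in a separate document that is not available here.

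Much of this stands, and it limits the point. It does not remove it. A listing is not a by-arm count. Per-protocol exclusion reasons mix AEs with other causes, and an infant in a neonatal arm who stops before dose 4 misses only placebo, so the three-dose criterion alone would not flag that infant. Whatever the endpoint list says, Protocol 13.4.2 names this summary, and the SAP text specifies a different one.

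The objection is also right about the data source. Protocol 11.3 requires actions taken to be recorded for each AE but does not say that the field identifies action on IP. That must be checked against the CRF.

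**Conclusion.** The SAP omits a safety summary that the protocol requires, puts a different one in its place and does not declare the change. As a result, no planned summary identifies infants who stopped IP because of an AE but stayed in the study. This should be corrected, but its reach is limited to safety reporting. The primary analysis, the sample size and the named safety endpoints are unaffected.

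A reader might infer more than the documents support, in four ways:
- **That these infants vanish from the tolerability tables.** They do not; they are in the safety set and their AEs enter the general tables.
- **That the withdrawal table is biased.** It is labelled as study withdrawal and measures that. The fault is an omitted summary, not a distorted estimate.
- **That the number of missed cases can be stated.** The documents give no expected rate of AE-driven stopping and no proportion remaining in follow-up, so any figure would be invented.
- **That every such infant will be classed as having completed the trial.** Protocol 6.12.1 asks for continued samples and the Diarrhoea Log, not expressly for every visit, and the classification rests on the End of Study page, which is not available here.

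The conclusion assumes that the SAP text governs the outputs and that the unseen table shells do not already restore the missing summary.

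**What to change.** 1. In SAP 16.1.3 and 16.1.8, add the number and percent of participants with an AE that led to IP being stopped permanently, on the safety set, by treatment group and dose. Keep the study-withdrawal row as a separate item.
2. State the derivation: the AE action-taken field together with the IP Administration form. First confirm that the CRF field identifies action on IP.
3. In SAP 10.1, report by arm the infants who discontinued IP but remained in the study, with the reason.
4. If the sponsor means to drop the protocol's summary, record and justify that in SAP section 5.

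The cost is SAP wording and about one extra table row, plus a disposition category. If the CRF field is adequate, no new data are needed. If it is not, the link has to be made from dosing records and the reasons recorded for stopping, and the SAP should say so. Trial conduct does not change.
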